## 11.3.3 Informed Consent

The consent process may differ somewhat by clinical site according to local IRB guidelines. The informed consent document will be structured such that it enables potential participants to indicate any aspect of the study with which they are not willing to be engaged. Separate consent forms will be provided for specific non-core tests or ancillary studies when appropriate. The informed consent will be available in Spanish and will cover all aspects of eligibility, risks and benefits of participation, confidentiality, withdrawal from the study, baseline testing and subsequent follow-up visits. Participants who turn 18 years old before the end of the study and have samples stored in the repositories will be re-consented per local IRB guidelines.

The Health Insurance Portability and Accountability Act (HIPAA) will affect the use or disclosure of protected health information in the CKiD study. Each clinical site may hold different requirements regarding HIPAA. Some institutions may request that this HIPAA language be inserted into the appropriate sections of the informed consent form; other clinical sites may require a stand alone document.

Consent must be obtained under circumstances that provide the prospective participant (if age appropriate) and parent or legal guardian sufficient opportunity to consider whether or not to participate and that minimize the possibility of coercion or undue

influence. Participants must also meet the inclusion and exclusion criteria to be enrolled in the study.

The physician or designee will explain the study and the procedures at the clinical site and provide ample time to the child and the parents to consider joining the study. Each patient's legal guardian will provide written informed consent prior to any study procedures. Assent will be obtained from minors according to the age guidelines set by the clinical site's local IRB. Consent forms are either read to the subject or guardian or given to them to read with ample opportunity to ask questions or obtain further explanation. Consent forms will explain all procedures to be performed during the study. It will be made clear to the prospective subjects that their refusal to participate in the study will in no way jeopardize the quality of medical care they will receive nor will agreement to participate prevent them from withdrawing consent at a future time.

## 11.3.3.1 Alternative Methods of Consent

The continued follow-up protocol will be completed via phone, in-person or on-line to collect long-term outcome data on individuals who no longer complete regular CKiD study visits because they initiate renal replacement, become pregnant or are lost to regular follow-up (LTRFU). The LTRFU population are subjects who are no longer completing regular study visits at the site because they are unable to be reached, are chronic no shows (i.e., frequently miss scheduled visits), have transitioned to adult care and/or relocated to locations where they are unable to travel to a CKiD clinical site. Specifically, the LTRFU population is difficult to retain in the continued follow-up protocol because obtaining written consent presents a significant barrier when research staff are unable to speak with participants face to face. With the development of the web-based continued follow-up survey, an "on-line consent" process presents a viable alternative method to written informed consent. Website consent statements have been developed to serve as the "Letter of Information" for participants. In addition, sites can explore other methods consenting individuals such as a verbal consent process over the phone.

For this LTRFU population who are no longer being seen at the site, the research cannot practically be conducted without an alternative to written consent. To implement this method of consent, sites will need to do the following:

- Request a waiver of documentation of informed consent
- Request a waiver or alteration of HIPAA from their local IRB
- Specify the plan for consenting subject in the IRB submission

## 11.3.4 Confidentiality

Protection of participants depends on the joint activities of all clinical sites, the clinical coordinating centers, the repositories as well as the DCC. Extensive efforts will be made to ensure that participants' confidentiality is maintained. Each participant is assigned a unique study identification number and is never tracked through the study by name, social security number, medical record number, or other distinct personal identifiers. A log of the participant names, participant ID numbers, and pertinent registration information (e.g. home address, telephone number, social security number and emergency contact information) is maintained in a locked area at each clinical site. The

CKiD Protocol OSMB Approved DCC, clinical coordinating centers and repositories do not have access to this log. Only the participant ID number (study ID) is given to the DCC, clinical coordinating centers and repositories; therefore, the study ID is the unique identifier for the data of a subject in the study's database. Any communication between the DCC, clinical coordinating centers and the repositories with the clinical sites regarding participant data will occur via the participant ID number. Any forms or documents sent to the DCC, clinical coordinating centers, repositories, IRB or Regulatory Authorities will have all personal identifying information removed. All research reports, articles, and presentations will report only aggregate findings.

A certificate of confidentiality will be obtained for the entire study from the National Institutes of Health. With this Certificate, the researchers cannot be forced to disclose information that may identify the participant, even by a court subpoena, in any federal, state, or local civil, criminal, administrative, legislative, or other proceedings. The researchers will use the Certificate to resist any demands for information that would identify the participant, except as explained below.

- The Certificate cannot be used to resist a demand for information from personnel of the United States Government that is used for auditing or evaluation of federally funded projects or for information that must be disclosed in order to meet the requirements of the federal Food and Drug Administration (FDA).
- The Certificate of Confidentiality does not prevent the participant or a member of their family from voluntarily releasing information about themselves or their involvement in this research. If an insurer, employer, or other person obtains the participant's written consent to receive research information, then the researchers may not use the Certificate to withhold that information.
- The Certificate of Confidentiality does not prevent the researchers from disclosing information about intent to hurt themselves or others that is disclosed by the participant or a member of the participant's family.

## 11.3.5 Adverse Events

This study is not a clinical trial; therefore, documentation of adverse events will be obtained within 24 hours of a study procedure. Adverse events are considered any undesirable clinical experience (i.e., increased heart rate or blood pressure) occurring to a patient within 24 hours of a study procedure. However, if a participant has a serious adverse event (SAE) related to a study procedure (i.e., iohexol GFR) within 24 hours of the procedure, the event should be reported within specified local IRB time guidelines to the local IRB and the DCC. For the purposes of this study, a SAE within 24 hours of the study procedure will be considered any event that results in death, is immediately life threatening, requires inpatient hospitalization, or results in persistent or significant disability/incapacity. Life threatening means the patient is at immediate risk of death from the event as it occurred. All SAEs related to a study procedure will be reviewed monthly by the Steering Committee and annually by the External Advisory Committee. If the clinical site becomes aware of the death of a study participant between study visits, local IRB procedures should be followed and the DCC informed of the event within 5 days.

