Because of the difficulties with administering and measuring inulin in children, standard endogenous creatinine clearances have been used to estimate GFR. However, it is well known that Creatinine is secreted, so that CCr exceeds CIn, particularly at low levels of GFR [Arant, Jr. 1972]. Exogenous tracers, such as I-iothalamate, Cr-EDTA, and 99mTc-DTPA yield clearance values exceeding those derived from standard inulin clearances due to renal tubular secretion [Rahn 1999, Silkalns 1973]. Moreover, despite the low dose of radioactivity in the tracers, it is unlikely that most families would approve of using repeated doses of radioactivity in their children for monitoring the progression of chronic kidney disease.

A reliable alternative to inulin clearance avoids both the use of radioactivity and continuous infusion of the marker. iohexol, a non-ionic, low osmolar, X-ray contrast medium (OmnipaqueR) that is safe and non-toxic and used for angiographic and urographic procedures, is eliminated from plasma exclusively by glomerular filtration [Back 1988]. Iohexol has a molecular weight of 821 daltons, a plasma elimination halftime of ~90 min, is distributed into the extracellular space and has less than 2% plasma protein binding [Back 1988, Krutzen 1984]. Iohexol is excreted completely unmetabolized in the urine with 100% recovery within 24 hours after infusion [Olsson 1983]. Since iohexol can be quantified in small samples, capillary, as well as venous, sampling can be employed [Krutzen 1990]. Extrarenal elimination of iohexol in a setting of reduced GFR is negligible [Nilsson-Ehle 1994]. Iohexol is measured in deproteinized plasma or serum. The commercially available preparations contain two isomers of iohexol, both of which are handled similarly by the body [Gaspari 1995, Krutzen 1990]. In practice the major peak, eluting at about 5 min, is used for clearance calculations [Gaspari 1995]. Most studies indicate close agreement between GFR (measured by inulin clearance) and clearance of iohexol, measured as standard urinary clearance, total body clearance, or plasma disappearance [Brown 1991,Erley 2001,Gaspari 1995,Olsson 1983,Rahn 1999].

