Using Cohort 1 and Cohort 2 iGFR measurements, investigators further examined simplifying the iohexol-based GFR component. For Cohorts 1 and 2, investigators concluded that sufficient iohexol-based GFRs have been measured to validate estimating equations across age and level of GFR except in those with higher levels of GFR [Schwartz 2012]. Available equations currently underestimates high values of iGFR, therefore to refine the estimating equation, continued measures of iohexol-based GFR are needed in participants with higher levels of GFR (i.e. GFR>90 ml/min|1.73m^2).

Therefore, iohexol-based GFR component will be continued in a sub-group of Cohort 1 and 2 participants identified as those who had iohexol-based GFRs  $\geq$  90 ml/min|1.73m^2 at their last study visit (as of December 2015). These participants will continue with iohexol-based GFR tests until their iGFR falls below 90 ml/min|1.73m^2. In addition, iohexol-based GFR tests will be optional for Cohort 3 participants.

*Processing blood collection and Make-up GFR*: The blood samples can be drawn by venipuncture or by inserting a second polyethylene catheter in the opposite antecubital vein (or any acceptable vascular access can be used.) Sampling cannot be performed through the catheter in which the iohexol was infused. These samples will be sent to the central biochemistry laboratory (CBL) for processing and analysis. In the event that the iohexol procedure cannot be completed during the study visit (i.e., IV infiltration of iohexol or inability to successfully draw all blood samples for iohexol), the participant ideally should be rescheduled for a make-up GFR within 3 months. The visit should not be repeated any sooner than 48 hours after the initial study visit if iohexol was infused. The B0 (blood collected pre-iohexol infusion for CBL chemistries, serum creatinine, cystatin C and iohexol blank) and first morning urine, if collected, must be sent to the CBL for processing and analysis. During the make-up GFR visit, a B0 blank (blood collected pre-iohexol infusion) and 2 blood samples for determining the iohexol concentrations will be collected.

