## 6.4.2.3 Home Blood Pressure Monitoring

Pending funding, home blood pressure measurements will be collected using QardioArm, which is a wireless blood pressure device validated for measuring blood pressure and heart rate in participants with an arm circumference of 22-35 cm. At selected sites, a pilot study will be conducted in which home BP measurements will be collected to assess the feasibility of obtaining home BP measurements among CKiD participants who have not initiated RRT. Home BP monitoring will be performed beginning at visit 2 and then every year thereafter. Participants will be given the QardioArm device to take home to collect data over the course of 3 days.

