### 6.5.2 Non-Core Tests

## 6.5.2.1 Physical Activity Monitoring

Pending funding, physical activity will be measured using an Actigraph Link device. The Actigraph Link device is an FDA-approved accelerometer frequently used for research purposes to assess physical activity. The device will be utilized to assess physical activity in a subset of participants at selected clinical sites. The device will collect 8 days of continuous wear data and monitoring will be performed at visit 1b and every year thereafter.

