## 11.3.1.2 Blood Draws

Drawing blood or inserting an IV catheter may cause faintness, inflammation of the vein, pain, bruising, infection or bleeding at the puncture site. The amount of blood drawn at each visit will not exceed the recommendations stated in TITLE 45—Public Welfare and Human Services Part 46—Protection of Human Subjects (i.e. the amount of blood to be collected may not exceed the lesser of 50 ml or 3 ml per kg in an 8 week period and collection may not occur more frequently than 2 times per week.)

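### Section 11.3.5 writes a 24-hour limit into the SAE definition and reporting trigger, so a serious procedure-related event that begins later falls outside SAE reporting and the stated committee review; the start of the window is also undefined

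*Protocol*

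**What the plan says.** Section 11.3.5 of the protocol applies the 24-hour limit at every step.

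- Documentation of adverse events is confined to the 24 hours around a study procedure, on the ground that the study is not a clinical trial.
- An adverse event is an undesirable clinical experience "occurring to a patient within 24 hours of a study procedure".
- The reporting trigger is a serious event "related to a study procedure (i.e., iohexol GFR) within 24 hours of the procedure". Such events go to the local IRB and the data coordinating center (DCC).
- The SAE definition repeats the limit: "a SAE within 24 hours of the study procedure will be considered any event that results in death", with immediate threat to life, inpatient admission and lasting disability as the other criteria.

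The section then assigns review of procedure-related SAEs to the Steering Committee (monthly) and the External Advisory Committee (annually). Separately, if a site learns of a death between visits, local IRB procedures apply and the DCC is told within 5 days.

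Section 11.3.1 presents its list of potential risks as study-related adverse events. Under it, section 11.3.1.2 says that blood draws and IV catheters "may cause faintness, inflammation of the vein, pain, bruising, infection or bleeding at the puncture site". Section 11.3.1.8 lists discomfort, bruising or arm injury for the home blood pressure device. Section 6.4.2.3 describes its use: "Participants will be given the QardioArm device to take home to collect data over the course of 3 days".

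**The concern.** The protocol names harms that its procedures may cause, then makes their status depend on the hour at which they appear. Relatedness and seriousness are not enough: an event that begins after 24 hours fails the definition even if the investigator is sure that the procedure caused it.

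What is at stake is the meaning of the SAE count. A low count of procedure-related SAEs would partly reflect the definition. It would then be a weak check on the statement in section 11.3.1.1 that the study carries minimal to moderate risk. Exposure is wide: blood is drawn at annual visits, iohexol visits ideally use two venous catheters, and Cohort 3 enrolls children from 6 months of age.

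The second problem is the missing anchor. For a blood draw, start and end nearly coincide. For a device used at home over several days they do not, and sites could apply the rule differently.

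**Working it through.** The plan gives no figure to reproduce. The check follows events through section 11.3.5 and then compares the window with the stated duration of device use.

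**Step 1: one event at different times.** Take a puncture-site infection, judged related to an iohexol visit and requiring admission.

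| Event | Meets AE definition | Meets SAE definition and trigger | In the stated committee review |
|---|---|---|---|
| Infection with admission, onset at hour 20 | yes | yes | yes |
| The same event, onset on day 3 | no | no | no |
| Procedure-related death on day 2, beyond 24 hours | no | no | no; the DCC is informed within 5 days |
| Mild vein inflammation at hour 20 | yes | not serious | no |
| Mild vein inflammation on day 3 | no | not serious | no |

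The first two rows differ only in onset time. The sentence on committee review does not repeat the 24-hour limit, but it speaks of SAEs, and the only SAE that the section defines is one inside the window. The last two rows show that mild events have no stated committee review whatever their timing, so the review gap created by the window concerns serious events.

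**Step 2: the home blood pressure device.** Inputs are the 24-hour window (section 11.3.5) and 3 days of use (section 6.4.2.3).

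- Duration of use: 3 × 24 = 72 hours.
- Window counted from the start: 24 / 72 = 33% of use covered; 72 − 24 = 48 hours not covered.
- Window counted as during use plus 24 hours after the end: it closes at 72 + 24 = 96 hours from the start; 72 / 72 = 100% of use covered.

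Section 11.3.5 does not say which reading applies.

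**Step 3: the share of serious events lost.** This would be the proportion of procedure-related serious events that begin after 24 hours. Section 11.3.1.2 lists infection and vein inflammation without onset times, so the documents support no value. The range is 0 (all begin inside the window) to 1 (all begin after it).

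**The case against.** The strongest defense is that the window is deliberate. The study is observational, section 11.3.5 gives that as the reason, and local IRB rules govern SAE timelines and deaths. Several routes also lie outside the window. Deaths that a site learns of reach the DCC. The monitoring board has a general remit in section 3.7.2 to review data for safety. Health care use is collected at annual interviews (section 6.1.3.2).

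Part of this stands. A reader might infer that catheter infection, vein inflammation and device injury never count and never reach safety review. That is too strong: any of them inside 24 hours counts, related serious ones are reviewed, and deaths are passed on whatever their timing. But the death clause does not cover non-fatal events and states no committee review. The board's remit does not create a record of an event that no rule requires to be recorded. Nothing in the health care utilization section links an admission to a study procedure. That the study is not a trial does not explain why a related serious harm should stop counting at hour 24.

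Other stronger readings also fail.

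- **Late iohexol events.** The protocol says iohexol "is eliminated from plasma exclusively by glomerular filtration" and, of a make-up measurement, "The visit should not be repeated any sooner than 48 hours after the initial study visit if iohexol was infused". A reader might infer slow clearance at low GFR and a 48-hour safety horizon. But the 48-hour rule concerns repeating a measurement, section 6.2.1.1 also states complete recovery within 24 hours, and section 11.3.1.1 names no delayed reaction. Retained tracer is not itself a harm.
- **Ambulatory monitoring.** It lasts 24 hours, no longer than the window.
- **Activity monitor.** "The device will collect 8 days of continuous wear data", but section 11.3.1.10 reports no confirmed side effects, so there is no listed harm to miss.
- **Onset after a day.** It may seem natural that most infections appear later than 24 hours, but the protocol does not say so.

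The device point therefore rests on the home blood pressure device alone, which is a pilot at selected sites, pending funding.

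**Conclusion.** The point holds in a limited form. By definition, a serious procedure-related event that begins after 24 hours is not an SAE in this study and is outside the review that section 11.3.5 assigns to the two committees, even when the harm is one that section 11.3.1.2 lists. This follows from the wording alone and needs no assumption about how often such events occur.

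The number of events affected is unknown and may be small. The one size that can be given is for the home blood pressure device: 24 of 72 hours covered if the window runs from the start, and all 72 if it runs through use and 24 hours beyond. The first figure depends on a reading that the protocol neither adopts nor excludes, which is why the anchor should be stated.

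This is a gap in safety capture. It does not show that any procedure is unsafe, and it does not affect the study's analyses of kidney, neurocognitive, cardiovascular or growth outcomes.

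**What to change.** Change section 11.3.5 in two places.

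1. Remove the 24-hour limit from the SAE definition and reporting trigger for events judged related to a study procedure. Such events are then reported, and reviewed by the Steering Committee and the External Advisory Committee, whenever the site learns of them. This also brings procedure-related deaths after 24 hours into the review.
2. Keep a 24-hour window for other adverse events, but state its anchor: it runs through the procedure or device use and for 24 hours after the procedure ends or the device is removed.

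Check the new text against sections 11.3.1.2, 11.3.1.8 and 6.4.2.3, so that the listed risks and the capture rule agree.

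The cost is protocol wording and a few more events to report and judge for relatedness. No visit, procedure or participant contact is added.

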## Appendix B: Study Proposal Form Chronic Kidney Disease in Children Cohort Study Concept Sheet Submission Form

#### Please fill out all the lettered and numbered sections below

(THIS FORM WILL NOT BE ACCEPTED UNLESS ALL OF THE FIELDS ARE COMPLETED)

This form is intended for use for all collaborations. Where "□" appears, double click on box and change default value from "not checked" to "checked".

## A. GENERAL INFORMATION

- 1. Date of submission: Click here to enter date.
- 2. Lead investigator(s): Click here to enter text.
- 3. Study Title: Click here to enter text.
- 4. Contact Person (if different from lead investigator): Click here to enter text.
  - a. Institution: Click here to enter text.
  - b. Address: Click here to enter text.
  - c. Telephone number: Click here to enter text.
  - d. Fax Number: Click here to enter text.
  - e. Email address: Click here to enter text.
- 5. Submission Type: Initial Revised [Double click box to add check] Addendum/Expansion of previously approved concept (Readme #\_\_\_)
- Summary of Changes: If submission is a revision (to a previously rejected) or an amendment (to a previously approved) existing concept sheet, please summarize all changes. (NOTE: In addition, please highlight or track all changes to the previously submitted concept sheet.)
- 7. Guideline (pages x x) have been reviewed:  $\Box$  Yes  $\Box$  No
  - By submitting this Concept, you agree to abide by the CKiD Publication Policy (https://statepi.jhsph.edu/ckid/investigator.html\_click on "Publication Policy"). The policy includes submitting manuscripts accepted for publications to NIHMS for PMCID number, if not using a NIH-approved PMC journal.
  - Productivity (e.g., preliminary data analysis, presentation, and/or publication) of approved Concepts is required within 3 years of approval; otherwise the topic may be reassigned.

